#### **E. Chart Review**

N/A. This study is not conducting a chart review or electronic medical records.

#### **F. Biospecimens**

IRB NUMBER: 14472  
IRB APPROVAL DATE: 08/28/2023

N/A. There will be no biospecimen collection in this study.

**G. Banking/Repository/Database**

All data collected during the study will be retained for future use in tobacco and nicotine research. Data will be stored electronically on a secure password server that can only be accessed by approved study personnel. No biospecimens will be collected or stored.

**H. Inclusion / Exclusion Criteria**

1. List the criteria that will define who will be **included** in the study
  - $\geq 18$  years old
  - Self-identify as sexual and/or gender minority
  - Reside in the State of Oklahoma
  - Report past 30 day use of combustible tobacco
  - Willing to quit using combustible tobacco within the next 2 weeks
  - English-speaking
  - Willing to refrain from smoking any substance, such as cannabis, within 48 hours of expired carbon monoxide collection
  - Willing to complete all intervention components and data collection activities
2. List the criteria that will define who will be **excluded** in the study.
  - Have contraindications for nicotine replacement therapy (NRT)
3. Provide early termination criteria.
  - Participants will be terminated at any point during their study participation if they have stopped participating study activities and are non-responsive to 3 or more consecutive contact attempts from research staff.

**I. Gender/Minority/Pediatric Inclusion for Research**

The study has no inclusion/exclusion criteria based on race/ethnicity. We are specifically recruiting for cisgender women (target 35% of the sample) and gender minority identified people (i.e., transgender, gender non-conforming, other gender; target 30% of the sample) given the sexual and/or gender minority focus of this pilot intervention. We do not anticipate difficulty achieving this gender composition given that cisgender women have been easier to recruit than cisgender men in our past studies on tobacco and/or cannabis use and our recruitment efforts will specifically target the gender and sexual minority

community in Oklahoma. The PI has developed a strong working relationship with local SGM-serving organizations in Oklahoma, including our community partner on this proposal (Freedom Oklahoma), and has successfully targeted sexual and/or gender minority participants through targeted social media campaigns and community partner recruitment in past studies. All materials will be tailored to low-literacy populations to enhance inclusion of under-represented populations and minority groups.

**J. Recruitment and Enrollment**

1. Describe the plans for recruitment.

a. Methods to identify and recruit potential participants

We will enroll participants (N=20) over a 4-month period and recruit through the Tobacco Treatment Research Program (TTRP), which serves an average of 30 sexual and/or gender minority (SGM) individuals per year without SGM-targeted recruitment efforts. We will supplement this pool of SGM participants by recruiting for SGM participants through local SGM-serving organizations, SGM targeted social media ads (e.g., Facebook), and snowball recruitment.

- Tobacco Treatment Research Program (TTRP) enrollments. The Stephenson Cancer Center's TTRP follows an Institutional Review Board (IRB)-approved research protocol where participants are referred by a health care provider through the University of Oklahoma Health Sciences Center (OUHSC) electronic medical record. Community participants may contact the clinic via the web, email, phone, fax, walk-in and tablet connection (in certain circumstances). The TTRP responds to referrals by providing information about treatment options, screening participants, and scheduling them for standard TTRP treatment or for an ongoing trial (if eligible and interested).
- Local sexual and/or gender minority (SGM)-serving organizations. Freedom Oklahoma, a SGM-serving organization in Oklahoma City and the community partner on this proposal (See Letter of Support) will distribute recruitment materials to their extensive professional networks and channels of communication and will connect the research team to additional SGM-serving community organizations as needed to diversify the sample. Physical materials with study information will be printed as needed for distribution by SGM serving community organizations in Oklahoma and posted in public spaces (e.g., palm cards, flyers).
- Targeted social media campaign. Participants will be recruited through paid advertisements on Facebook and Instagram that target SGM people who use tobacco and live in Oklahoma using a well-established campaign program managed by the University of Oklahoma Marketing team. Additional recruitment advertisements will be posted on Craigslist or other local advertising services and online forums as needed.
- Snowball recruitment. Participants will be invited and incentivized (\$25 per referral of an eligible individual who enrolls in the study for a maximum of two

referrals and \$50 additional at the end of their participation in the study) to share the study information and/or [name] contact information with anyone they think may be eligible and interested in participating in the study.

2. Describe the consent procedures to be followed

Informed consent. All study advertisements will provide a link to the study's REDCap website with a short eligibility questionnaire. If respondents are eligible, they will be taken to the informed consent webpage, where will have the opportunity to consent. [name] contact information will be made available to participants to answer any questions about the study and to provide a way to inform the researchers at any point should they wish to withdraw from the study or have changed their minds about the use of their data. All materials will be tailored to low-literacy populations (i.e., a 4th grade reading level).

Participants will be reminded that their participation is voluntary. Additionally, they will be reminded that they are allowed to discontinue participation in the study at any time, without any loss of benefits or other negative consequences. Individuals will be given as much time as they need to make a decision about participation; they will initiate their own consent on the informed consent at any time that they wish. The participant will be given a copy of the consent form to keep for his or her records. All research team members will complete an approved course on the protection of human subjects and be trained on how to clearly describe study procedures and the obtain informed consent process.

3. Describe the location where consent is most likely to take place. Consent will most likely take place in the participants' own home or any other location where they are accessing the consent webpage on their own device without the presence of a researcher.

4. Describe provisions for recruiting non-English speaking participants. This study will not recruit non-English speaking participants.

5. Describe measures to decrease participant coercion.

Several recommended approaches will be used to reduce coercion, including allowing participants ample time to review the consent, and using only qualified trained research staff to engage in the consent form process.

Further, participants will be told in writing at the screening and at the time of consent that their participant is completely voluntary. They will be reminded during phone calls/video chat interactions with research staff and before and during the in-depth interview that they can decline to answer any question and they can withdraw their participation at any time without penalty.

## **K. Risks and Benefits**

1. Describe risks and assess their likelihood and severity.

**The primary risks to participants are discomfort, loss of confidentiality, and medical side effects from FDA-approved Nicotine Replacement Therapy (NRT).**

Discomfort may be experienced during participation in empowerment activities or the in-depth interview discussion, or due to some of the questionnaire items administered over the study period.

A potential, although unlikely, risk to participants is loss of confidentiality. The severity of harm in the case of loss of confidentiality may range from mild to severe depending upon the individual and the specific circumstances. However, the risks of participation in the study are similar to that of participation in standard care, as loss of confidentiality may be experienced in either case. In addition, participant data residing on laptop/tablet computers and smart phones will be encrypted and password protected.

There is a risk of side effects associated with FDA-approved tobacco cessation medications; Nicotine Replacement Therapy (NRT):

- Possible risks of the nicotine patch include: increased blood pressure; skin redness, swelling, or rash; irregular heartbeat or palpitations; or symptoms of nicotine overdose including nausea, dizziness, weakness, and rapid heartbeat; and vivid dreams or sleep disturbance.
- Possible risks of nicotine gum include: increased heart rate and blood pressure; mouth, teeth, and jaw problems; irregular heartbeat or palpitations; symptoms of nicotine overdose including nausea, vomiting, dizziness, weakness, and rapid heartbeat; or allergic reaction such as difficulty breathing or rash.
- Possible risks of nicotine lozenges include: increased heart rate and blood pressure; mouth, teeth, and jaw problems; indigestion or sore throat; irregular heartbeat or palpitations; symptoms of nicotine overdose including nausea, vomiting, dizziness, weakness, and rapid heartbeat; or allergic reaction such as difficulty breathing or rash.

Nicotine replacement medications may have enough medication to make children and pets sick.

2. Describe procedures for protecting against or minimizing potential risks.

a. Address measures instituted to protect the privacy and/or confidentiality of participant PHI

Detailed protocols are in place to assess participant safety and respond effectively throughout participant engagement in this empowerment-enhanced tobacco cessation intervention pilot study, and to minimize risk of loss of participant confidentiality and data storage procedures.

**General Procedures:** Each participant will be assigned an identification number that will be utilized in place of names in all electronic and print data

files. The file containing the links between participant names and identifiers will be kept in a separate password-protected file, which will be destroyed 12 months after the completion of the study. Any print information will be stored in a locked filing cabinet in the Principal Investigator's locked office. Electronic data (with names omitted) will be maintained on the investigator's computers, and all computers and electronic files will be password protected. Biochemical verification of smoking status will be collected in a private room in the TTRP. All project staff will complete extensive training focused on each of the following topics: 1) project rationale and objectives, 2) the informed consent process, 3) general data collection procedures (e.g., computer data collection, privacy), and 4) use of the carbon monoxide monitor.

**Minimizing risk of participant discomfort and side effects from FDA approved Nicotine Replacement Therapy (NRT):**

Participant safety and level of distress will be assessed through research team members' and TTRP counselors' direct interactions with participants over video chat or in-person (including during interviews), on the phone, and during email correspondences. Specific protocols for participants who request substance use dependence treatment support, appear heavily intoxicated, and/or appear suicidal are provided below.

The Tobacco Treatment Research Program (TTRP) tobacco cessation assistance activities – including tobacco cessation counseling, biochemical verification of smoking status, nicotine replacement therapy, and administration of follow up surveys - follows a University of Oklahoma Health Sciences Center Institutional Review Board (IRB)-approved research protocol (PI: [name]).

This study will not enroll individuals with contraindications for Nicotine Replacement Therapy (NRT).

Participants will be told prior to starting the study that their participation in research is voluntary and they may stop at any time. Prior to beginning each empowerment activity participation session and the interview they will be reminded that they may choose to stop or pause the activity/interview at any time and may decline to answer any questions or engage in any activity that causes them discomfort. If a participant becomes distressed during the empowerment activity or interview they will be offered the option to stop or pause.

Empowerment activity debriefing sessions. Following each empowerment activity participation session, the empowerment activity facilitator (a member of the [name] research team) will engage participants in a debriefing session to reflect on their experiences participating in the activity and any emotions or topics that arose for them. During this debriefing session, and during any other point of contact with participants, the activity

facilitator and research team will follow the protocol for ‘Vulnerable Subjects’ as needed (described below).

**Minimizing risk of loss of participant confidentiality and data storage procedures:**

All information obtained from participants will be kept completely confidential. Data will be stored as follows:

- **All data will be stored in secure locations to minimize the risk of breach of confidentiality**, including locked file cabinets and password-protected computers and databases. Adverse events will be reported to the University of Oklahoma Health Sciences Center IRB, as appropriate, to ensure the safety of subjects’ information.
- **All study questionnaires** will be administered online with participants’ own devices or a study device using an electronic data capture system (REDCap) to maintain 21 CFR Part 11 compliance and Good Clinical Practice (GCP) standards.
- **All transcripts from interviews will be stored on encrypted hard drives** disconnected from the Internet and kept in locked file cabinets.
- **Human subjects will be assigned coded participant ID numbers.**
- **Files with identifying information will be stored separately** from files with other forms of data (e.g., substance use status, mobility data, transcripts).
- **Access to individually identifiable private information about human subjects will be had only by the individuals listed in this proposal.**
- **Study investigators have completed required University of Oklahoma Health Science Center training and certification** in the conduct of research with human subjects.

**Vulnerable Subjects:**

This study focuses on tobacco cessation and empowerment for sexual and/or gender minority people in Oklahoma. Specific protocols will be in place to protect participant safety. **See protocol in Data and Safety Monitoring Plan, below.**

**Clinical Resource to the Research Team:** [name] will serve as the clinical resource to the research team for this pilot study (PhD in Counseling Psychology, University of Oklahoma; [name]; [name]). [name] is the Director of the Oklahoma Tobacco Helpline and Assistant Professor at the University of Oklahoma Health Sciences Center. He is a Licensed Psychologist whose expertise includes suicide prevention. [name] will train [name] and the rest of the research team in the study protocols designed to minimize risk to participants (described below) and will be available to the study team to discuss the protocols as needed throughout the duration of the study.

3. Describe potential benefits and importance to the participants and others. Potential benefits to participants include individual empowerment outcomes (e.g., more active coping strategies for minority stressors) and the possibility that the empowerment-enhanced tobacco cessation intervention will have a beneficial impact on smoking cessation outcomes.

4. Discuss why risks are reasonable in relation to benefits.

The knowledge gained from this study may be utilized to enhance efficacy of tobacco cessation assistance for sexual and/or gender minority (SGM) people, improve smoking abstinence rates in SGM populations, and thereby reduce tobacco-related disease and health disparities.

#### **L. Multiple Sites**

N/A. This study does not involve multiple sites.

#### **M. Statistical Methods**

Provide biostatistical design, power calculations determining the number of participants, and the proposed analysis.

[name], biostatistician, is a Co-Investigator on this project and informed the design of the statistical methods for this study.

This is a pilot study to assess feasibility and acceptability of an intervention.

Sample Size/Analysis Plan. Primary outcome variables will be: retention, perceptions of the intervention, adaptive coping strategies, biochemical verification of tobacco abstinence at 12 weeks post-quit-date, and treatment adherence. We will evaluate retention by calculating the proportion of participants who complete the final study visit at 12-weeks post-quit, with the goal of retaining >80% of participants. We will qualitatively evaluate perceptions of the intervention (as described above). We will use a two-sided paired samples t-test to examine the mean differences in adaptive coping strategies pre- and postintervention ( $\alpha=0.05$ ). Assuming 20% attrition and a standard deviation of differences of  $4.0^{85}$ ,  $n=20$  participants will provide 80% power to detect a mean difference of 2.6 in adaptive coping strategies. Tobacco cessation outcomes will be considered successful if the proportion of participants with biochemicallyverified smoking abstinence (expired carbon monoxide) at 12 weeks post-quitedate is equal to or greater than the general TTRP sample (i.e., 18% at 12 weeks). Treatment adherence will be considered successful with all participants having >50% of treatment weeks with an MAQ score indicating moderate/high adherence and counseling session attendance.

Expected outcomes: Empowerment-enhanced tobacco cessation assistance will be acceptable and feasible (Aim 1), will increase within-subject empowerment and

improve cessation predictors (Aim 2), and will meet benchmarks for tobacco cessation outcomes (Aim 3).

**N. Data and Safety Monitoring Plan**

Continuous monitoring and reporting of events will be undertaken by the Principal investigator ([name]) and unanticipated problems will be promptly reported to the IRB. Since the standard smoking cessation treatment is offered by the Stephenson Cancer Center independent of this research proposal, adverse event monitoring will focus on events related to empowerment activity participation and study assessments. Possible adverse events might include compromised data security, and severe emotional reactions by participants due to participation in SGM social change mobilization and community building activities and/or questionnaire items.

**Participant Safety Monitoring Plan:**

This study focuses on tobacco cessation and empowerment for sexual and/or gender minority people in Oklahoma. Specific protocols will be in place to protect participant safety. See below.

**Clinical Resource to the Research Team:** [name] will serve as the clinical resource to the research team for this pilot study (PhD in Counseling Psychology, University of Oklahoma; [name]; [name]). [name] is the Director of the Oklahoma Tobacco Helpline and Assistant Professor at the University of Oklahoma Health Sciences Center. He is a Licensed Psychologist whose expertise includes suicide prevention. [name] will train [name] and the rest of the research team in the study protocols designed to minimize risk to participants (described below) and will be available to the study team to discuss the protocols as needed throughout the duration of the study.

**PROTOCOL FOR REQUESTS FOR SUBSTANCE USE DEPENDENCE TREATMENT AND/OR CRISIS SERVICES:**

Upon request, participants will be given the contact information for resources from the Substance Abuse and Mental Health Services Administration:

- FindTreatment.gov - Millions of Americans have a substance use disorder. Find a treatment facility near you.
- Suicide prevention lifeline [name] Free and confidential support for people in distress, 24/7.
- National Helpline [name] Treatment referral and information, 24/7.
- Oklahoma-specific Google map that allows users to select which type of resource they need, and then see which facilities in OK are licensed by ODMHSAS:<https://www.google.com/maps/d/u/0/viewer?mid=137cjQWot11ah4uYf2vIE7hjRGU&ll=35.62854113370643%2C98.30299192656254&z=7>

**PROTOCOLS FOR HEAVILY INTOXICATED PARTICIPANTS:**

IRB NUMBER: 14472  
IRB APPROVAL DATE: 08/28/2023

During any point of contact with the research team or TTRP staff, participants may be heavily intoxicated and/or express thoughts of suicide or related ideation or thoughts of harming self-suggestive of suicidal risk. Participant safety will be monitored by researchers during in-person, phone, or email contact with participants.

**Below are protocols to be followed for heavily intoxicated and/or suicidal participants:**

Warning Signs for Intoxication

- Unsteady gait
- Breath that smells of alcohol

If a participant is heavily intoxicated or high at the time of participation, there are two issues that must be considered. First there is the issue of whether the participant should complete the study activity or return/reengage at a later date. The researcher/staff will need to make a judgment as to whether the participant can continue based on such factors as their ability to understand and complete activities, forms or interviews. The second issue to consider in the case of inperson data collection is whether the individual is safe to travel home at the end of the activity or assessment (if occurring in person).

If the participant traveled from their home to another location for the study activity (e.g., our offices, the TTRP clinic) and there is any concern about the participant's ability to get home safely or if the participant discloses that they are too "high" or intoxicated to continue with the assessments, the researcher/staff should secure safe transportation home for the participant and reschedule the assessment process.

*"I am concerned that you may be intoxicated right now. Is that true?"*

If true, then you may say:

*"If you are intoxicated, I don't think this is a good time for us to continue with the interview/activity. But I am concerned about how you are going to get home safely. It is the study's policy for you to stay here until you are okay to drive home. We are going to help arrange transportation."*

1. Notify [name] by calling her at (cell) [contact].
2. Give [name] the participant's name, and any other relevant information you have. Ask for assistance in arranging for transportation.
3. Have the participant talk with [name] over the phone, via video chat, or in person.
4. Stay with participant (in person or virtually) until transportation arrives.

Note: If the participant refuses this transportation assistance and insists on driving in an intoxicated state, they should be informed that the police will be called and a description of their car given and the direction it is heading.

## PROTOCOLS FOR SUICIDAL PARTICIPANTS:

### Acute Suicidal Warning Signs

- The participant expresses hopelessness (e.g., “I’ll never get better”).
- The participant makes direct or indirect statements about killing themselves, being better off dead, or things being better for others if participant wasn’t alive

If any participant makes a direct or indirect statement about suicide, hopelessness or death, even when said in a joking or off hand manner, this is a cause for concern. Sometimes suicidal people leave hints. It is not true that a person who talks frequently about committing suicide will not do it. Some keep their suicidal thoughts to themselves, while others do not. If a participant shows a desire or intent to kill her/him/their self, s/he/they should be evaluated by a qualified clinician to determine her/his/their level of risk and be connected to treatment setting that can ensure their safety. If you suspect that a person is in danger of killing her/him/their self, the interview should be stopped and specific focus should be made on the participant’s safety, and the protocol below should be followed:

To start, you should say:

*“I am concerned about what you just said to me about your feelings/thoughts right now (e.g., “feeling so bad that you wish you were dead” or “thinking things are hopeless or would be better if you weren’t around”). I think this is really important. I need to connect you with someone to talk to who can help. I can give you the National Suicide Prevention Lifeline number for you to call privately, or we can do it together if that would be helpful.”*

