### Step-by-step process

1. Stop the interview/activity
2. Express concern for participant’s safety and well-being and the importance of getting participant the help they need to get through this difficult time (see script above)
3. Encourage the participant to call the hotline and/or offer to call together:
- Toll-free, 24-hour hotline of the **National Suicide Prevention Lifeline [name]**  
Your call will be connected to a trained counselor at a suicide crisis center nearest you.[https://suicidepreventionlifeline.org/?utm\\_source=google&utm\\_medium=web&utm\\_campaign=onebox](https://suicidepreventionlifeline.org/?utm_source=google&utm_medium=web&utm_campaign=onebox)
4. If the participant won’t call and/or disconnects the call and won’t reconnect, and you are concerned they are in imminent danger of hurting themselves or others, stay on the phone with them and ask them to “hold while you make a call to get some help to them.”
5. Call 9-1-1 and request a CIT officer make a welfare check on an individual expressing an imminent desire to kill themselves. Cooperate with the 91-1 operator to provide details about participant’s location and specific

statements that caused you to believe the individual was at imminent risk of suicide.

6. If the participant is still on the phone, reassure them that you will stay on the phone until the help arrives. Wait with the participant on the line until they confirm the CIT officer has arrived at their location.

7. Immediately following a referral to the suicide prevention lifeline or a 9-11 welfare check call:

- If in TTRP, inform TTRP supervisor on-call and inform them of the situation
- If not in TTRP, call [name] at [contact] (cell) and inform her of the situation

8. After you provide participant support and have informed either the TTRP supervisor or [name], document the incident in RedCap in the participant's file.

9. The day following the incident, attempt to call the participant to follow up and schedule next study visit and/or leave a message requesting participant reach out when able.

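### The steps for a suicidal participant can be followed exactly without anyone arranging the clinician evaluation the protocol calls for, or learning whether the Lifeline was reached

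*Protocol*

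**What the plan says.** The relevant text is in Protocol section N; the SAP does not address it.

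Under Acute Suicidal Warning Signs, a participant who shows a desire or intent to die by suicide should be "evaluated by a qualified clinician to determine her/his/their level of risk and be connected to treatment setting that can ensure their safety". No role is named for either task. The section then sends staff to a script and a list of steps. The script includes this offer: "I can give you the National Suicide Prevention Lifeline number for you to call privately". It also offers to make the call together.

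The Step-by-step process has nine steps:

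- Steps 1 and 2: stop the activity and express concern.
- Step 3: "Encourage the participant to call the hotline and/or offer to call together".
- Steps 4 to 6: the 9-1-1 route. Step 4 applies when the participant will not call, or breaks off and will not reconnect, "and you are concerned they are in imminent danger of hurting themselves or others". Step 5 requests a welfare check by a CIT officer. Step 6, if the participant is still on the phone, reads: "Wait with the participant on the line until they confirm the CIT officer has arrived at their location".
- Step 7: "Immediately following a referral to the suicide prevention lifeline or a 9-11 welfare check call", staff inform the on-call TTRP supervisor or, outside TTRP, a study contact.
- Step 8: document the incident in REDCap.
- Step 9: on the next day, "attempt to call the participant to follow up and schedule next study visit and/or leave a message requesting participant reach out when able".

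The consent statement printed after the steps says that if staff are concerned about danger of suicide and the participant does not agree to call the Lifeline or 9-1-1, the protocol requires staff to call 9-1-1. It does not carry step 4's condition that the danger be imminent.

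**The concern.** The protocol sets its own standard, clinician evaluation and connection to care, and then gives staff a list that does not carry the standard through. Staff who do everything on the list can end an incident not knowing whether a participant with suicidal intent spoke to anyone qualified. Activities may be conducted remotely (section D, Potential problems and alternative strategies), so the participant may be alone and off site when contact ends.

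What is at stake is participant safety. No endpoint, sample size or analysis is affected. Section N does anticipate severe emotional reactions as a possible adverse event, so the situation is foreseeable even if uncommon.

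**Working it through.** No arithmetic applies. The check sets the standard beside the steps, follows particular participants through them, and then looks for other text that closes the gap.

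**Standard against steps.** The standard has two parts: evaluation by a clinician and connection to a treatment setting. Read one by one, none of the nine steps mentions either part, gives anyone the job of arranging it, or asks whether it took place. Step 3 describes the person answering the hotline as a trained counselor. Step 6 confirms that an officer has arrived, not that an evaluation followed. Step 7 informs someone and gives that person no task.

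**A participant who calls the Lifeline with staff.** Staff witness the contact, so it is at least known that the Lifeline was reached.

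**A participant who takes the number to call privately.** The script permits this. The participant has not refused and has not broken off a call, so step 4 is not triggered and steps 5 and 6 do not follow. Steps 7 and 8 inform and document. Step 9 requires an attempt at contact, does not say to ask about the Lifeline or care, and by its and/or wording can be met by leaving a message. Full compliance is possible without anyone learning whether the call was made.

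**A participant who declines to call but is not judged in imminent danger.** Step 4 needs both the refusal and the concern about imminent danger, so it does not escalate. The consent statement tells the same participant that 9-1-1 will be called. The two texts give staff different instructions. Counting the offered number as a referral, so that steps 7 to 9 still apply, the incident ends in the same place: informed, documented, and perhaps a message left.

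**Other text that might close the gap.**

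- Protocol for requests for treatment or crisis services (section N): "Upon request, participants will be given the contact information for resources from the Substance Abuse and Mental Health Services Administration". This depends on the participant asking.
- Clinical Resource to the Research Team (sections K and N): a licensed psychologist with suicide-prevention expertise trains staff in these procedures and can be consulted about them. No role during an incident is stated. The step 7 contact appears to be someone else, since the protocol uses different pronouns for the two.
- Opening of section N: the principal investigator monitors events and reports to the IRB. That is oversight, not arranging care.
- Section K, on minimizing discomfort: staff and counselors assess distress during contacts, and the debrief after each empowerment activity refers back to the vulnerable-subjects protocol, which is this same list.
- Protocols for heavily intoxicated participants: safety is monitored during contacts. For intoxication the steps do close the loop: staff notify a specific person, ask for help arranging transport, have the participant speak to that person and stay until transport arrives. The list for suicidal participants has no counterpart for evaluation and care.

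**The case against.** The strongest reply is that the sentence on clinician evaluation is general guidance and the nine steps are how non-clinical staff pursue it, by handing the participant to crisis services. On that reading the Lifeline or the welfare check is the route to evaluation, and only a confirmation prompt is missing. Much of this stands. Both are real hand-offs that may lead to evaluation. But the protocol does not say that they satisfy the standard, and even if they do, nothing confirms that a private caller used the first of them.

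A second reply is that context reduces the gap. The psychologist trains the team, and training may settle what a follow-up call covers. Six weekly counseling sessions and repeated surveys mean step 9 is often not the last contact. TTRP activities run under a separate IRB-approved protocol that is not among these documents, so an on-call supervisor may have further duties there. These points stand as mitigation. They do not close the gap: later contacts are not scripted for this purpose, and the TTRP protocol would not necessarily reach incidents outside TTRP.

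A reader might infer that the study has no suicide safety plan, or that nobody is responsible for anything after an incident. The documents do not support that: they contain warning signs, a script, a hotline offer, 9-1-1 escalation, notification, documentation, next-day contact and disclosure in the consent form. Nor should one count the routes through the steps and read the fraction left unconfirmed as a measure of risk. Such counts describe the list, not how often participants would take each route.

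**Conclusion.** The point holds as a gap in closing the loop. The protocol calls for clinician evaluation and connection to care, and its steps can be followed exactly without anyone arranging these or learning whether the Lifeline was reached. The participants affected are the one who takes the number to call privately and the one who declines without being judged in imminent danger. For the second, step 4 and the consent statement also disagree.

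The size can be stated only in procedural terms. The documents give no incident rate for the planned 20 participants, and there may be no incident at all. The change is still worth making, because a missed case would be serious and the remedy is small. The conclusion assumes that staff act on the written list alone; training content and the separate TTRP protocol could reduce the gap in practice but cannot be seen here. Nothing in the documents supports requiring a further clinician whose availability is unknown.

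**What to change.** 1. **Step 9.** Before scheduling the next visit, ask whether the participant reached the Lifeline, was evaluated and was connected to care. Record the answer in REDCap with the incident. State that a message alone does not complete the follow-up.
2. **Step 7.** Have the person informed also notify the licensed psychologist already named as clinical resource, who advises on evaluation and referral.
3. **Step 4 and the consent statement.** Make the two agree on when 9-1-1 is called for someone who declines to call, and in particular on whether imminent danger is required.

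The cost is a minor protocol and consent amendment, a short update to staff training, and a small amount of the psychologist's time per incident. The psychologist's availability during incidents is not documented and should be confirmed first. Scheduling the next visit may take longer after an incident.
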